The proposed study will randomize people with serious mental illness to I-IMR (n=300) and CDSMP (n=300) to address the following four specific aims and hypotheses:

Aim 1: Compare the effectiveness of I-IMR to CDSMP with respect to our primary ***physical health self-management outcomes***.

Hypothesis 1: I-IMR compared to CDSMP will be associated with greater improvements in ***physical health self-management abilities*** (Self-Rated Abilities for Health Practices scale; SRAHP, and a qualitative interview) and ***physical health consumer activation*** (Patient Activation Measure; PAM); and (secondary hypothesis) greater improvement in self-reported ***physical health*** functioning (PROMIS Global Health measure).

Aim 2: Compare the effectiveness of I-IMR to CDSMP with respect to our primary ***mental health self-management outcomes***.

Hypothesis 2: I-IMR compared to CDSMP will be associated with greater improvements in ***mental health self-management abilities*** (Illness Management and Recovery Scale; IMRS, and a qualitative interview); and ***mental health consumer activation*** (PAM-MH); and (secondary hypothesis) greater improvement in self-reported ***mental health*** (PROMIS Global Health measure).

Aim 3: Compare the effectiveness of I-IMR to CDSMP with respect to ***emergency room and acute care hospital days***, and risk of ***10-year cardiovascular mortality***.

Hypothesis 3: Participation in I-IMR compared to CDSMP will be associated with fewer emergency room admissions and acute care hospital days over 12 months compared to the 12 months before participation; and greater reduction in 10-year cardiovascular risk score (ACC/AHA Cardiovascular Risk Score) from baseline to 12 months.

Aim 4: Compare I-IMR to CDSMP with respect to subgroup differences in self-management outcomes by **mental illness subgroup** (schizophrenia-spectrum vs. mood disorders) and by **age group** (18-49 vs. 50+).

Hypothesis 4: Comparing I-IMR and CDSMP, the difference in treatment effects will be greater for people with schizophrenia spectrum disorders compared to mood disorders; and greater for older (age 50+) compared to younger (18-49) participants with respect to: **physical health self-management abilities and activation** (SRAHP; PAM); **mental health self-management abilities and activation** (IMRS; PAM-MH); and 10-year ***cardiovascular risk reduction*** (ACC/AHA Cardiovascular Risk Score).

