COVID-19 Enhancement Primary Aim: After co-design of the 3-session I-IMR module, we will evaluate the impact of the module by comparing participants assigned to I-IMR (n=75) to participants assigned to CDSMP (n=75) on the primary and secondary outcomes (**primary**: knowledge and use of measures to prevent contracting and spreading COVID-19; **secondary**: use of healthcare services for COVID-related concerns; perceived isolation and social disconnectedness).

Primary Hypothesis: I-IMR participants will demonstrate greater improvements in their scores on the primary outcome measure (a measure of knowledge and behaviors to prevent contracting and spreading COVID-19 developed for this project) compared to CDSMP participants.

Secondary Hypothesis: I-IMR compared to CDSMP participants will demonstrate less COVID-related health care service use and greater improvements in social connectedness.

Exploratory Aim: Explore differential response with respect to race/ethnicity (Black versus White adults); age (older versus younger adults); and psychiatric diagnosis (schizophrenia-spectrum vs. mood disorders).

Exploratory Hypothesis: Effect sizes for the I-IMR module versus generic support calls alone will be even greater among Blacks v. Whites, older (55+) v. younger adults, and people with schizophrenia-spectrum v. mood disorders.

3. Study Design

The proposed study is to compare I-IMR and CDSMP in improving outcomes of importance to the target population of people with SMI: optimizing personal physical and mental health, being an active agent in determining personal physical and mental health wellness goals, decreasing risk of early mortality, and minimizing use of the ER and hospitals. A secondary objective is to learn whether psychiatric diagnosis and/or age interacts with treatment, specifically, whether treatment effects vary more for participants with schizophrenia or older age. Consistent with a truly pragmatic trial, inclusion criteria are broad and exclusion criteria are limited. Participants will be randomized, stratified by diagnosis (schizophrenia spectrum vs. mood disorder) and age group (age 18-49 vs. age 50+).

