Study participants will be 600 adults age 18+ with SMI (diagnosis of schizophrenia, schizoaffective disorder, bipolar disorder, chronic depression with moderate impairment in functioning, PTSD, and/or other serious anxiety disorders (e.g., Generalized Anxiety Disorder, OCD, Panic Disorder, Agoraphobia, etc.) receiving services at Centerstone (TN) and Seven Counties Services (KY) who reflect the racial, cultural, linguistic, and ethnic diversity of people with SMI in this agency. The race/ethnicity of consumers is as follows: White: 61%, Black: 30%, Hispanic: 3%, Other: 6%; 95% English speaking; and 52% Female. Eligibility for the study also includes: diagnosis of a chronic medical condition increasing risk of early mortality from cardiovascular or respiratory disease or diabetes, hyperlipidemia, hypertension, COPD [including emphysema], asthma, coronary artery disease, heart failure, tobacco dependence, obesity), chronic pain, and at least 1 ER visit or hospitalization within the past year (and/or 3 or more unscheduled outpatient visits) or judgment by the treatment team of substantial need for illness self-management training. Consumers who do not speak English will be excluded for logistical reasons. Consumers with either no, or a well-controlled medical condition will not be included. Individuals residing in a nursing home or other institution will be excluded given the focus on independent management of illness. Because I-IMR and CDSMP involve learning new skills, individuals with a chart diagnosis of dementia, or evidence of significant cognitive impairment as indicated by the Saint Louis University Mental Status Examination⁷³ score <20, will be excluded. Temporarily, during the COVID-19 pandemic, we will use the Telephone Interview for Cognitive Status (TICS)¹²⁰ because the SLUMS cannot be administered over the phone.

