Overview of the Stanford Chronic Disease Self-Management Program (CDSMP): CDSMP is a 6-session group-based educational program co-delivered by two peers (lay people who have successfully managed a chronic illness) or a peer and a medical professional.^{21,22} This 6-week program covers techniques for dealing with problems such as: frustration, fatigue, pain and isolation; appropriate exercise for maintaining and improving strength, flexibility and endurance; appropriate use of medications; communicating effectively with family, friends and health professionals; nutrition; and evaluating new treatments (see Table 2). A meta-analysis of 23 studies of the CDSMP program *in general populations* conducted by the Centers for Disease Control and Prevention in 2013 found 4-6

| | | |
|--|---------------------------------------|---|
| -Identifying Common Problems | -Problem Solving | -Making Informed Treatment Decisions |
| -Differences between Acute and Chronic Illnesses | -Better Breathing | -Depression Management |
| -Using Your Mind to Manage Symptoms | -Pain and Fatigue Management | -Positive Thinking |
| -Making an Action Plan | -Endurance Activities | -Guided Imagery |
| -Dealing with Difficult Emotions | -Future Plans for Health Care | -Working with Your Health Care Professional |
| -Intro to Physical Activity and Exercise | -Healthy Eating Communications Skills | -Looking Back and Planning for the Future |
| | -Medication Usage | |

month improvements in energy, fatigue, self-rated health, aerobic exercise, cognitive symptom management, psychological health, communication with physicians, and health care utilization.⁶² CDSMP is currently offered in over 45 states and over 19 countries.

Table 2: The Stanford Chronic Disease Self-Management (CDSMP) Curriculum

4. Analysis

Evaluation of Group Equivalence.

Subgroup analysis for treatment effects (i.e., estimate of the treatment effect for each subgroup) is a common approach for HTE analysis. However, this approach is susceptible to the issue of multiple post hoc analyses. We have a total of 20 subgroup analyses (5 outcome measures by 4 subgroups), thus we will adjust the p-value to account for multiple tests for each subgroup analysis and use the false discovery rate method⁹⁰ implemented in SAS software.⁹¹ Subgroup analysis may increase the

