Analysis for Aim 4: In **Aim 4**, we compare I-IMR to CDSMP with respect to subgroup differences in self-management outcomes by ***mental illness subgroup*** (schizophrenia-spectrum vs. mood disorders) and by ***age*** (18-49 vs. 50+) based on our belief that greater cognitive limitations and comorbid health conditions may require more intensive and specialized self-management training consistent with I-IMR. We hypothesize that when comparing I-IMR and CDSMP, the difference in treatment effects will be greater for schizophrenia spectrum disorders compared to mood disorders; and greater for older (age 50+) compared to younger (age 18-49) participants with respect to: ***physical health self-management abilities and activation; mental health self-management abilities and activation*** and 10-year ***cardiovascular mortality risk reduction***. In this aim, we examine heterogeneity of treatment effects (HTE) using subgroup analyses. Because we pre-specified the 2 subgroups (diagnosis and age) and hypothesized the differential treatment effect between subgroups based on the literature, our approach is confirmatory (hypothesis driven) HTE analysis. To test HTE, we will use the same analytic models, GLMM for **Aim 1**, **Aim 2** and **Aim 3**, but we will include 3-way interaction terms (arm*time*group) in each model. A significant 3-way interaction effect will indicate the existence of the heterogeneity of treatment effects between subgroups. Following this step, we will conduct simple effect analysis to estimate treatment effect differences (a difference in slopes by time effect between arms) within each subgroup. Although our HTE analysis is hypothesis driven, we will report p-values for hypothesis testing for all subgroup analyses. We will also evaluate HTE by examining the magnitude of treatment effects with standard errors (clinically meaningful effect sizes) as outlined in PCORI Methodology Standards⁸⁸ and recommended by statisticians.⁸⁹

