600 Adults 18+ and 150 of consented participants will also participate in the COVID-19 enhancement.

b. Provide a justification of the proposed sample size

The sample size is based on maintaining an adequate sample for data analyses with consideration to retention based on previous studies. Retention in our previous studies and in our IIMR studies has been very high. We conservatively estimate a loss of 20% over the 12-month study, resulting in full follow-up data on $n = 480$.

c. Define the target population:

The target population are individuals diagnosed with a SMI (diagnosis of schizophrenia, schizoaffective disorder, bipolar disorder, chronic depression with moderate impairment in functioning, PTSD, or other serious anxiety disorders) with co-morbid chronic medical problems receiving services at Seven Counties Services (KY) and Centerstone (TN) who reflect the racial, cultural, linguistic, and ethnic diversity of people with SMI in this agency.

Inclusion and Exclusion Criteria: Eligibility for the study also includes: diagnosis of a chronic medical condition increasing risk of early mortality from cardiovascular or respiratory disease or diabetes, hyperlipidemia, hypertension, COPD [including emphysema], asthma, coronary artery disease, heart failure, tobacco dependence, obesity), chronic pain, and at least 1 ER visit or hospitalization within the past year (and/or 3 or more unscheduled outpatient visits) or judgment by the treatment team of substantial need for illness self-management training. Consumers who do not speak English will be excluded for logistical reasons. Consumers with either no, or a well-controlled medical condition will not be included. Individuals residing in a nursing home or other institution will be excluded given the focus on independent management of illness. Because I-IMR and CDSMP involve learning new skills, individuals with a chart diagnosis of dementia, or evidence of significant cognitive impairment as indicated by the Saint Louis University Mental Status Examination⁷³ score <20 , will be excluded. Temporarily during the COVID-19 pandemic, participants who score <20 on the TICS will be excluded.

d. Vulnerable populations

Note: Certain populations are considered vulnerable to coercion and undue influence and are provided with additional protections when participating in a research study.

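### Participants who qualify on PTSD or an anxiety disorder alone fit neither level of the diagnosis factor used for stratification and for the confirmatory Aim 4 contrast

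*Combined protocol and SAP*

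**What the plan says.** **Who is eligible.** Section 3 (Study Design) lists schizophrenia, schizoaffective disorder, bipolar disorder, chronic depression, "PTSD, and/or other serious anxiety disorders (e.g., Generalized Anxiety Disorder, OCD, Panic Disorder, Agoraphobia, etc". Section 9, item c (target population), repeats the list and ends it with "PTSD, or other serious anxiety disorders) with co-morbid chronic medical problems". Both lists are joined so that any one diagnosis is enough. The opening background is narrower: it describes serious mental illness by the first four diagnoses only.

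**How participants are stratified.** Section 3: "Participants will be randomized, stratified by diagnosis (schizophrenia spectrum vs. mood disorder) and age group (age 18-49 vs. age 50". The diagnosis factor has two levels.

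**How Aim 4 uses diagnosis.** Hypothesis 4 in Section 2 states that "the difference in treatment effects will be greater for people with schizophrenia spectrum disorders compared to mood disorders". Section 4, Analysis for Aim 4, says "our approach is confirmatory (hypothesis driven) HTE analysis", because the subgroups were specified in advance. The method reuses the Aim 1 to 3 models, "but we will include 3-way interaction terms", followed by effects within each subgroup. Under Evaluation of Group Equivalence, a subgroup analysis is the "estimate of the treatment effect for each subgroup", and the count is given: "We have a total of 20 subgroup analyses (5 outcome measures by 4 subgroups". A false discovery rate adjustment follows.

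**The full-sample rule.** Analysis for Aim 1 states that all analyses use the full sample by intention to treat. The models for Aims 1, 2 and 3(2) list arm, time and their interaction as fixed effects; neither stratification factor appears.

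**The concern.** A two-level rule is applied to a population with at least three kinds of member. Someone whose only qualifying diagnosis is PTSD, panic disorder or OCD has neither a schizophrenia-spectrum nor a mood disorder. The stratification rule as written cannot be applied to that person, and neither can the Aim 4 contrast.

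Each way of handling these people has a consequence that the plan does not acknowledge. Counted as mood, they make the five mood-disorder estimates and the five diagnosis interaction tests describe a mixture under a label that does not fit it. Left out, they make the diagnosis contrast depart from the full-sample rule. A second gap is that eligible diagnoses may be combined, yet nothing says which one decides the group when a person has, for example, both a schizophrenia-spectrum and a mood diagnosis.

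At stake is the meaning of an analysis presented as confirmatory because its subgroups are pre-specified. A subgroup without a membership rule is only partly pre-specified. The COVID exploratory hypothesis in Section 2 uses the same diagnosis contrast and has the same gap.

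**Working it through.** **1. The plan's own figures.** Completers: 600 × (1 − 0.20) = 480, as Section 9 states. Subgroup analyses: 5 outcomes × 4 subgroups = 20, as Section 4 states. The four subgroups are two diagnosis levels plus two age levels, so the count leaves no room for a third diagnosis group.

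**2. The texts side by side.** Eligibility admits PTSD/anxiety-only participants. Stratification, Hypothesis 4, Analysis for Aim 4 and the count of 20 all have two diagnosis levels. There is no *other* level, no primary-diagnosis rule, no ranking, and no statement that these participants are outside the contrast.

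**3. Assumed shares.** The documents give no diagnosis mix. Let *p* be the PTSD/anxiety-only share (assumed 5-20%, mid-case 10%) and *s* the schizophrenia-spectrum share (assumed 30-50%, mid-case 40%).

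- Without a defined stratum: 600 × 0.05 = 30 to 600 × 0.20 = 120 randomised; 480 × 0.05 = 24 to 480 × 0.20 = 96 completers.
- Share of a combined mood group with no mood disorder, p/(1 − s): 0.05/0.70 = 7%; mid-case 0.10/0.60 = 17%; 0.20/0.50 = 40%.

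**4. Precision if they are left out rather than called mood.** With nS schizophrenia-spectrum, nM mood and nP PTSD/anxiety-only completers (total 480):

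- SE ratio of the diagnosis contrast = √[(1/nS + 1/nM) / (1/nS + 1/(nM + nP))]
- SE ratio of the mood-subgroup estimate = √[(nM + nP)/nM]

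| s, p | nS, nM, nP | Contrast | Mood subgroup |
|---|---|---|---|
| 30%, 5% | 144, 312, 24 | 1.011 | 1.038 |
| 40%, 10% | 192, 240, 48 | 1.039 | 1.095 |
| 30%, 20% | 144, 240, 96 | 1.058 | 1.183 |
| 50%, 20% | 240, 144, 96 | 1.155 | 1.291 |

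**5. Lesser point: strata absent from the linear models.** If the strata explain a share R² of the variance of measured slopes, the reported SE is too large by k = 1/√(1 − R²). Type I error is then 2[1 − Φ(1.96k)], and a nominal 80% power becomes Φ(2.80 − 1.96k).

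| R² (assumed) | k | Type I error | Power |
|---|---|---|---|
| 0.01 | 1.005 | 0.049 | 79.7% |
| 0.02 | 1.010 | 0.048 | 79.4% |
| 0.05 | 1.026 | 0.044 | 78.5% |

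The value 0.05 is already generous. Visits at 0, 1/3, 2/3 and 1 year give a sum of squares of 0.556. An assumed residual variance of 0.3 contributes 0.3/0.556 = 0.54, and an assumed true slope variance of 0.1-0.4 brings the total to 0.64-0.94. Reaching R² = 0.05 then needs a strata variance of 0.034-0.049, which is 25% down to 11% of true slope variance: 0.034/0.134 and 0.049/0.449. If the strata affect level only, the SE changes by about 0.1% or less under the same kind of assumptions.

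**The case against.** The strongest reply is that Aim 4 can be read as using the stratum assigned at randomisation. The factor has two levels, Aim 4 names the same two, and the full-sample rule implies that everyone is in one of them. Group membership would then be fixed before any outcome existed, so a reader who infers that the analyst is free to choose membership after seeing results goes further than the text supports. That part of the objection stands: if assigned stratum is used, the post hoc risk shrinks. But the plan does not say that it is used, and this reading does not repair the label, since a mood group holding people with no mood disorder is still misdescribed. That these people were in fact placed in one of the two strata is itself an inference, because an undocumented third level is possible.

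It can also be said that parts of the statistical text seem to be absent: the Group Equivalence heading is followed by subgroup text, and some listed references on covariate adjustment are never cited. That is a reason for caution, but no visible text supplies a placement rule or the strata terms.

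Finally, no single ranking of diagnoses follows from the documents. Several rules are defensible, including a third level, which would take the count from 20 to 5 × 5 = 25. What is needed is one stated rule.

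**Conclusion.** The conflict between eligibility and the two-level diagnosis factor is real, and it affects the meaning of the Aim 4 diagnosis contrast. Its size is unknown. Under the assumed shares, 7-40% of a combined mood group would have no mood disorder (mid-case 17%), or the contrast SE would be 1-15% larger if they are left out (mid-case 4%). The 40% and 15% figures need both shares at their upper limits. The effect of unranked multiple diagnoses cannot be sized.

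Three stronger readings are not supported:

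- *That the main comparisons are compromised.* Allocation is still randomised and the full sample is still analysed, so Aims 1 to 3 remain valid.
- *That the rest of Aim 4 is either wholly safe or wholly affected.* The schizophrenia-spectrum estimates are unaffected only if no PTSD/anxiety-only participant was placed in that stratum. The age-subgroup results may shift through the false discovery rate adjustment if its family is all 20 analyses, which the text leaves unclear.
- *That omitting the strata biases the models or inflates false positives.* It causes no bias. In the linear models the test is slightly conservative, and only if the strata predict change over time. No harm is shown for the Aim 3(1) count model, the beta alternative for Aim 3(2) or the COVID model, so no change is asked of them.

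**What to change.** 1. Before outcomes are examined by arm, record the stratum actually used at randomisation for every PTSD/anxiety-only and multi-diagnosis participant. Write one placement rule for later enrolments, stating which diagnosis decides when there are several.
2. At the same time, fix Aim 4 membership so that each label matches who is in the group. Either compare schizophrenia spectrum with mood disorder, with PTSD/anxiety-only participants outside this contrast, or compare schizophrenia spectrum with all other eligible diagnoses and relabel the second group. Report the option not chosen as a sensitivity analysis, and apply the same rule to the COVID exploratory diagnosis contrast. Under either option the count stays at 20.
3. As a lesser step, add diagnosis and age stratum as randomised, with their time interactions, as fixed effects in the linear Aim 1 and Aim 2 models, and in Aim 3(2) when the identity link is used.

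The cost is protocol and SAP wording, a look-up of strata already assigned, one sensitivity analysis and a few model terms. No new data are needed and nobody's allocation changes. If PTSD/anxiety-only participants are left out of the main contrast, its SE rises by the 1-15% shown above and that of the mood-subgroup estimates by 4-29% (mid-case 10%), relative to counting them as mood; the alternative analysis uses everyone.

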This study will compare two commonly used but substantially different, evidence-based self-management interventions. **Integrated Illness Management and Recovery (I-IMR)**^{9,11} is an individually-tailored, 16-session, integrated program combining **both *physical and mental health self-management*** specifically developed for people with SMI. In contrast, the **Stanford Chronic Disease Self-Management Program (CDSMP)**^{21,22} is a group-based, 6-session, chronic disease self-management program largely focused on ***physical health self-management alone***. I-IMR is delivered by community mental health providers or by community outreach workers, while CDSMP is co-delivered by two peers or by a health professional and a peer.

In response to the COVID 19 pandemic, starting on March 13, 2020, we pivoted in-person delivery of all study group interventions and assessments to phone or video conference (Zoom). Beginning in July 2021, one of our sites (TN) will resume in-person services, so groups will revert to in-person (with remote assessments continuing for the time being). The other site has no established timeline for resuming in-person services, but we anticipate this happening at some point in the future, before the end of the study period. Given the unpredictable nature of the pandemic and our established experience and procedures for delivering the groups and assessments in-person or remotely, we plan to include language in the consent form explaining that the mode of delivery will depend on the status of the pandemic and whether services are being provided remotely or in-person. This will allow us to nimbly shift between remote and in-person as needed when and if abrupt changes related to the pandemic occur at the study sites, thus minimizing any interruption in delivery of study activities. For remote groups, participants will receive the intervention handouts in advance by mail so that they can read from and refer to them as they would during an in-person session. They will also receive a handout with instructions for successfully participating in research assessments and joining groups remotely. The same group leaders trained to deliver the interventions in person will deliver them remotely. Supervisors at Dartmouth will review video-recordings of remote groups whereas in-person groups will be audiotaped only for fidelity monitoring purposes.

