Intervention fidelity will be measured but not controlled; likewise, participant engagement will be measured but not required. The interventions will be delivered by community providers as part of routine services at Centerstone TN and Seven Counties Services in Kentucky to maximize generalizability of findings. Mixed quantitative and qualitative methods will be used to assess outcomes. Trained raters will administer in-person assessments at baseline, 4, 8, and 12 months. A sub-sample of participants will be invited to participate in a qualitative interview to describe their treatment experience. Temporarily, during the COVID-19 pandemic, the assessments will be conducted by telephone instead of in person. Participants due for assessments will receive a packet of the response options that are normally presented to them during the assessments and instructions for phone-based interviews. Research staff will mail them a gift card (instead of cash) when they complete their assessments.

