likelihood of Type II error due to small sample sizes. Therefore, we will not rely on statistical tests and p-values alone to evaluate HTE; we will rely on estimated effect sizes (estimate divided by the standard deviation) and compute confidence intervals around these effect sizes.

Evaluation of Attrition

We will recruit 600 participants and randomly assign them to two arms with equal allocation (300 per arm). Based on previous experience, we assumed 20% attrition by 12 months. In addition to enhancing the process of full informed consent, these procedures are designed to decrease the likelihood of study attrition due to inadequate appreciation of the time, effort, and component activities involved in participating in the intervention program, or in the study protocol.

Analyses for Primary Study Aims and Hypotheses

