Analysis for Aim 1: All analysis will be conducted on the full sample regardless of exposure to treatment (intent to treat). Our **primary hypothesis** in **Aim 1** is that I-IMR compared to CDSMP will be associated with greater improvements in physical health self-management abilities (Self-Rated Abilities for Health Practices) and physical health consumer activation (Patient Activation Measure). To test this hypothesis, we will fit generalized linear mixed-effects linear models (GLMM) with identity link functions and normal distribution specification. Treatment arm (I-IMR and vs. CDSMP), time (baseline, 4-, 8- and 12-month), and arm-by-time interactions will be specified as fixed effects. Intercept and time will be specified as random effects to take the correlated nature of the data resulting from repeated measures into account. The primary hypothesis of interest will be examined by testing if the arm-by-time interaction effect (difference in rate of improvement over 12 month) is significantly different from zero. Our **secondary hypothesis** is that I-IMR compared to CDSMP will have greater improvement in self-reported **physical health** functioning (PROMIS Global Health Measure). The same GLMM model will be used to test this hypothesis. Qualitative data for Aims 1 and 2 will be audio-recorded, de-identified and transcribed, and analyzed with ATLAS.ti using the “grounded theory” approach.⁸⁵ The Research Support Team will read data and develop operational definitions from transcript coding, a validated approach which allows for multiple perspectives.⁸⁵ Codes will be assigned to text, grouped, and checked for themes. The codebook will consist of *a priori* researcher-driven codes, derived from interviews and inductively derived codes from qualitative data.⁸⁵ Analyses will assess within group consensus or disagreement. Member checking will be employed to validate qualitative results and resolve any incongruent findings.

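### The Aim 1, 2 and 3(2) models leave out the stratification factors and site; adding them is a nearly free gain in precision, not a repair of bias

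*Combined protocol and SAP*

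**What the plan says.** **Randomisation.** Section 3 (Study Design) states: "Participants will be randomized, stratified by diagnosis (schizophrenia spectrum vs. mood disorder) and age group (age 18-49 vs. age 50" and over). Site is not named as a stratum. Section 4, Evaluation of Attrition, adds: "We will recruit 600 participants and randomly assign them to two arms with equal allocation (300 per arm").

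**Sites.** Section 3 also states: "The interventions will be delivered by community providers as part of routine services at Centerstone TN and Seven Counties Services in Kentucky".

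**Models.** Section 4, Analysis for Aim 1, states: "Treatment arm (I-IMR and vs. CDSMP), time (baseline, 4-, 8- and 12-month), and arm-by-time interactions will be specified as fixed effects". It continues: "Intercept and time will be specified as random effects to take the correlated nature of the data resulting from repeated measures into account". The primary test is of the arm-by-time term. Aim 2 uses the same approach. The cardiovascular-risk part of Aim 3, called Aim 3(2) here, repeats the same three fixed effects.

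**Where covariates do appear.** The service-use part of Aim 3, called Aim 3(1) here, tests the arms for balance on demographic and clinical covariates. Depending on the result, it adds covariates or uses inverse probability weighting; site is not named. Aim 4 brings in diagnosis and age through a three-way interaction with arm and time.

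**Delivery mode.** Section 2 says all group interventions and assessments went remote from March 13, 2020. Later it says: "Beginning in July 2021, one of our sites (TN) will resume in-person services, so groups will revert to in-person". For Kentucky: "The other site has no established timeline for resuming in-person services". The same sentence adds that a return in person is expected there too before the study ends.

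**The concern.** Stratified randomisation takes the variation between strata out of the arm difference. A model without the strata still counts that variation as noise, so its standard error is larger than the true sampling variation of the estimate. The trial then forgoes some of the precision that its own design bought.

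Aim 4 hypothesises that the treatment effect differs by diagnosis and age. If it does, change over time differs by stratum in at least one arm, and the primary models leave that difference in the residual.

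Site is a weaker case of the same kind. It is not balanced by design, but if change over time differs between the agencies, a site-by-time term would explain some of the residual variance.

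What is at stake is modest: some power, and intervals slightly wider than they need be. The available text gives no power, alpha or detectable effect for the main trial, so no stated margin shows that the loss can be ignored.

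**Working it through.** **1. The plan's own figure.** Section 9, item b, says: "We conservatively estimate a loss of 20% over the 12-month study". Then 600 × (1 − 0.20) = 480, or 240 per arm. The stated 480 reproduces.

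**2. Assumptions, because the documents give none.** Two-sided alpha 0.05; outcome scaled to the SD of participant change; R² = share of the variance of change explained by the added factors, taken as 1, 5 and 10%; sites of equal size. The arithmetic is for the identity-link models.

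**3. Unadjusted reference.** Standard error = √(2/240) = 0.0913 SD. Difference detectable with 80% power = (1.960 + 0.842) × 0.0913 = 0.256 SD.

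**4. Effect of adjustment.**
- Interval width ratio, unadjusted to adjusted = 1/√(1 − R²).
- Detectable difference = 0.2557 × √(1 − R²).
- Power at 0.256 SD = Φ(2.802/√(1 − R²) − 1.960).
- Type I error of the unadjusted test with fully balanced factors = 2 × [1 − Φ(1.960/√(1 − R²))].

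| R² | Width ratio | Detectable difference, adjusted | Power, adjusted | Type I error, unadjusted |
|---|---|---|---|---|
| 1% | 1.005 | 0.254 | 80.4% | 4.9% |
| 5% | 1.026 | 0.249 | 82.0% | 4.4% |
| 10% | 1.054 | 0.243 | 84.0% | 3.9% |

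The comparison figure of 80% is nominal. If the factors are fully balanced, actual unadjusted power is Φ(0.842/√(1 − R²)) = 80.1, 80.6 and 81.3%. The gain is then 0.3, 1.4 and 2.7 points, against 0.4, 2.0 and 4.0 if they are not balanced.

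**5. Site by chance alone.** The SD of the between-arm difference in site share is √(0.25 × 4/600) = 4.1 points at 600 and √(0.25 × 4/480) = 4.6 points at 480. A site difference in change of 0.2 or 0.5 SD then moves the arm contrast with SD 0.2 × 0.0456 = 0.009 or 0.5 × 0.0456 = 0.023 SD. The standard error is 0.091 and already covers this.

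**6. Simulation.** 4,000 trials per setting, 480 complete cases, blocks of 4 within diagnosis × age, arm contrast of participant slopes. With complete balanced data this matches the planned arm-by-time test with time as a linear slope. Within-factor slope SD is 1, and every setting has a 1 SD site difference in level.

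| Slope effects | True arm effect | Rejection, unadjusted | Rejection, adjusted |
|---|---|---|---|
| none | 0 | 5.1% | 5.2% |
| site 0.5 SD only | 0 | 4.5% | 4.3% |
| site, diagnosis, age, 0.5 SD each | 0 | 4.1% | 5.6% |
| site, diagnosis, age, 0.2 SD each | 0.256 SD | 78.7% | 79.5% |
| site, diagnosis, age, 0.5 SD each | 0.256 SD | 74.9% | 80.9% |

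Under the null, mean estimates were about 0 throughout. With all three effects at 0.5 SD, the unadjusted model's standard error averaged 0.0994 against an empirical 0.0944, about 5% too wide. That setting is R² = 0.1875/1.1875 = 15.8%, above the range in step 4; the 0.2 SD setting is 0.03/1.03 = 2.9%.

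**The case against.** The strongest reply is that little is lost. Every factor effect above is assumed, and at the low end the gain is under one power point. The error is in the safe direction. Aim 3(1) already allows covariates, and Aim 4 already puts diagnosis and age into models for the same self-management outcomes and cardiovascular risk. All of that stands, and it limits this to an improvement. It does not remove the point: the Aim 4 models answer the subgroup question, the Aim 3(1) clause depends on observed imbalance, and neither reaches the primary Aim 1 and 2 tests.

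Three stronger readings are tempting, and the documents do not support them.

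- **Site or delivery mode biases the arm comparison.** Randomisation is of individuals, so site and calendar-driven mode are related to arm only by chance. Constant site differences in level drop out of the arm-by-time test, and the standard error already carries the chance imbalance in site-specific change.
- **Site is the same as delivery mode.** Both sites went remote together and both are expected to return. They differ only for a period of unstated length from July 2021, so a site term would not stand in for mode.
- **The trial cannot show effects by site.** Site is known for every participant, so results by site can be reported. They are simply not prespecified.

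One practical objection also stands. Eligibility includes PTSD and other serious anxiety disorders, which fit neither named diagnosis stratum. The covariate must therefore be the stratum actually used at randomisation.

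**Conclusion.** This is a free improvement. The primary Aim 1 and 2 models and the Aim 3(2) model omit the factors used to stratify, and omit site. There is no bias and no excess of false positives.

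For R² of 1 to 10%, intervals are 0.5 to 5.4% wider than with adjustment, and power at 0.256 SD rises from a nominal 80% to 80.4 to 84.0%. The unadjusted type I error of 4.9 to 3.9% assumes that all the added factors are fully balanced. Only diagnosis and age are balanced by design; omitting the unstratified site leaves type I error near nominal and costs precision alone. The simulated power gains run from under 1 to about 6 points.

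These figures rest on assumed factor effects, equal sites, complete data and an identity link. The size under the log-link count models of Aim 3(1), or the beta option of Aim 3(2), was not computed.

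**What to change.** - In the Aim 1, Aim 2 and Aim 3(2) models, prespecify diagnosis stratum, age stratum and site as fixed effects, each with its interaction with time. The time interactions matter: with complete balanced data, main effects alone would leave the arm-by-time test unchanged.
- Define diagnosis stratum as the one used at randomisation, and state how participants with PTSD or another anxiety disorder were assigned to it.
- In Aim 3(1), include the same terms regardless of observed imbalance.
- Report the arm-by-time effect within each site, labelled descriptive.

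The cost is SAP wording and a few degrees of freedom, fixed before the outcome data by arm are seen. Site, age and the stratum assigned at randomisation should already be on record. Adding site as a randomisation stratum for participants not yet enrolled is optional; the fix does not need it.
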